3.7.4.1. Hypothesis and/or Parameters to Be Estimated

This objective is descriptive and no statistical hypothesis test will be performed.

3.7.4.2. Sample Size Consideration

There was no sample size calculation for this objective.

3.7.4.3. Endpoint Definition

The endpoint is the KM event rate of new permanent pacemaker implant at 30 days post-procedure.

3.7.4.4. Data Collection and Analysis Methods

Data will be collected on a site reported permanent pacemaker implant form. As described in section 3.5, a Kaplan-Meier analysis will be performed for the event rate of new permanent pacemaker implant at 30 days post-procedure. This objective will be analyzed for the safety analysis set defined in section 3.4.

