APPENDIX G. EVENT CODE LIST

The following information will be kept separate from the CIP and independently provided to the investigators. The sponsor will maintain updated lists.

- List of names and addresses of the investigation sites in which the clinical study will be conducted
- Initial list of names, addresses, and professional positions of clinical investigators, principal clinical investigators and coordinating clinical investigators
- List of names and addresses of other institutions involved in the clinical study
- Case Report Forms. CRFs shall be developed to capture the data for each enrolled subject as required by the CIP. The CRFs shall include information on the condition of each subject upon entering, and during the course of, the clinical study, exposure to the investigational device/product and any other therapies
- Instructions For Use
- Investigators Brochure

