APPENDIX G. EVENT CODE LIST

Myocardial Infarction

- 100 Peri-procedural myocardial infarction
- 101 Spontaneous myocardial infarction

Stroke and TIA

- 102 Disabling stroke: ischemic
- 103 Disabling stroke: hemorrhagic
- 104 Disabling stroke: undetermined origin
- 105 Non-disabling stroke: ischemic
- 106 Non-disabling stroke: hemorrhagic
- 107 Non-disabling stroke: undetermined origin
- 108 Transient ischemic attack

Bleeding Complications

- 110 Life threatening or disabling bleeding event
- 111 Major bleeding event
- 112 Minor bleeding event

Acute Kidney Injury

- 113 Acute kidney injury: stage 1
- 114 Acute kidney injury: stage 2
- 115 Acute kidney injury: stage 3

Vascular Access and Access Site Complications

Major

- 120 Major vascular complication: aortic dissection, aortic rupture, LV perforation, or new apical aneurysm/pseudoaneurysm
- 121 Major vascular complication: access site or access site-related vascular injury (dissection, stenosis, perforation, etc)
- 122 Major vascular complication: distal embolization from vascular source
- 123 Unplanned endovascular or surgical intervention
- 124 New ipsilateral lower extremity ischemia
- 125 Surgery for access site-related nerve injury
- 126 Permanent access site-related nerve injury
- 127 Other major vascular complication

Minor

- 130 Minor vascular complication: access site or access site-related vascular injury
- 131 Minor vascular complication: distal embolization from vascular source
- 132 Unplanned endovascular stenting or unplanned surgical intervention not meeting criteria for major complication
- 133 Vascular repair or need for vascular repair
- 134 Other minor vascular access site complication
- 140 Failure of closure device leading to alternative treatment

Other TAVI-Related Complications

- 150 Conversion to open surgery
- 151 Unplanned use of CPB
- 152 Coronary artery obstruction
- 153 Ventricular septal perforation
- 154 Mitral valve apparatus damage or dysfunction
- 155 Cardiac tamponade
- 156 Prosthetic valve thrombosis
- 157 Valve migration
- 158 Valve embolization
- 159 Ectopic valve deployment
- 160 TAV in TAV deployment
- 161 Major hemolysis
- 162 Minor hemolysis
- 163 Prosthetic valve endocarditis: definite
- 164 Prosthetic valve endocarditis: possible
- 165 Major frame fracture
- 166 Minor frame fracture
- 167 Other TAVI-related complication

Conduction Disturbances and Arrhythmias

- 170 Atrio-ventricular block, 1°
- 171 Atrio-ventricular block, 2°

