3.2. Baseline Characteristics

Baseline demographic and clinical variables will be summarized for the attempted implant analysis set (safety set) as defined in section 3.4.

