3.4. Analysis Sets

Subjects who are taken to the procedure room for implantation will comprise the study population evaluated for the study objectives and associated endpoints.

The analysis sets are further defined as follows:

- **Safety Set (Attempted Implant):** The safety set includes all subjects who are brought into the procedure room for implantation.
- **Device Success/ Hemodynamic Performance Set (Implanted):** The device success/ hemodynamic performance set includes all subjects who are implanted with the Evolut R TAV, defined as the Evolut R TAV is placed in the aortic annulus and completely released from the EnVeo R catheter delivery system.

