3.7.3.4. Data Collection and Analysis Methods

The CEC codes for the VARC-2 Combined Safety Endpoint:

- All-cause mortality (CEC Death Form)
- All stroke (disabling and non-disabling) (CEC: 102 to 107)
- Life-threatening bleeding (CEC: 110)
- Acute kidney injury: stage 2 or 3 (including renal replacement therapy) (CEC: 114 to 115)

- Coronary artery obstruction requiring intervention (CEC: 152)
- Major vascular complication (CEC: 120 to 127)
- Valve-related dysfunction requiring repeat procedure (BAV, TAVI, or SAVR)
 - Catheter intervention to repair or replace Evolut R
 - Surgery intervention on Evolut R

As described in section 3.5, a Kaplan-Meier analysis will be performed for the VARC-2 Combined Safety Endpoint at 30 days post-procedure and for each individual component. These objectives will be analyzed for the safety analysis set defined in section 3.4.

3.7.4. Secondary Objective #5 (Safety) - Event Rate of New Permanent Pacemaker Implant at 30 Days

This objective is to characterize the event rate of new permanent pacemaker implant at 30 days.

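### The 30-day new-pacemaker rate is planned only in the full safety set and 'new' is not tied to baseline pacemaker status, so the rate in patients who could receive a first device is not estimated

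*SAP*

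**What the plan says.** Protocol 2.2.3 lists the 30-day rate of new permanent pacemaker implant as a secondary safety endpoint. SAP 3.7.4.3 makes it a Kaplan-Meier quantity: "The endpoint is the KM event rate of new permanent pacemaker implant at 30 days post-procedure". SAP 3.7.4.4 gives the source, "Data will be collected on a site reported permanent pacemaker implant form", and the population, "This objective will be analyzed for the safety analysis set defined in section 3.4". SAP 3.4 defines that population: "The safety set includes all subjects who are brought into the procedure room for implantation". Protocol 2.7.4 assigns the same population to all study objectives, so the SAP follows the protocol here.

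Neither document states what 'new' means:

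- The exclusion criteria (Protocol 3.2, repeated in SAP section 2) name a prior mechanical aortic valve but not a prior pacemaker.
- Protocol Appendix E has no pacemaker definition.
- Protocol Appendix G lists codes 170 to 189 under "Conduction Disturbances and Arrhythmias", with no pacemaker code.
- The Kaplan-Meier rules in SAP 3.5 do not remove subjects with an existing device from the risk set.

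The case report forms are kept apart from the protocol. Its appendices section says only that "CRFs shall be developed to capture the data for each enrolled subject as required by the CIP".

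**The concern.** A patient who arrives with a permanent pacemaker cannot receive a first one. Kept in the denominator with no possible event, such patients pull the rate below the rate among those who can have the event. If instead sites enter generator replacements or upgrades on the form, the count mixes in events that are not first implants. The text does not say which applies.

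This matters because Protocol 1.1 names the need for new pacemaker insertion as a remaining challenge of the procedure. It also names conduction disturbance related to implant depth as a risk that repositioning may mitigate. The rate in patients without a device addresses that question directly. The planned rate also moves with the share of enrolled patients who already have one, and a reader can undo this only if that share is reported.

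**Working it through.** The plan gives no expected rate, sample size or precision for this endpoint (SAP 3.7.4.1 and 3.7.4.2), so there is no figure to reproduce.

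**Inputs.** N = 1000, the approximate number of implanted subjects (SAP section 2); the safety set may be slightly larger. The remaining inputs are assumptions:

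- p, baseline pacemaker prevalence: 5, 10, 15, 20%.
- r, 30-day rate of first implants in patients without a device: 10, 15, 20%.
- q, proportion of patients with a prior device whose replacement is recorded as 'new': 0 or 2%.

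**Formulas.**

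- Reported safety-set rate = r(1 − p) + qp.
- Gap to the at-risk rate = r − [r(1 − p) + qp] = p(r − q).
- Whole-set 95% half-width = 1.96 × √[w(1 − w)/1000], with w = r(1 − p).

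The rate formula is exact when nobody is censored before day 30. It is approximate if censoring differs by baseline status.

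**Replacements not counted (q = 0).** Gap in percentage points, with gap divided by half-width in brackets:

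| p | r = 10% | r = 15% | r = 20% |
|---|---|---|---|
| 5% | 0.50 (0.28) | 0.75 (0.35) | 1.00 (0.41) |
| 10% | 1.00 (0.56) | 1.50 (0.71) | 2.00 (0.84) |
| 15% | 1.50 (0.87) | 2.25 (1.09) | 3.00 (1.29) |
| 20% | 2.00 (1.19) | 3.00 (1.49) | 4.00 (1.76) |

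Example: with p = 10% and r = 20%, the reported rate is 0.20 × 0.90 = 18.0%. The half-width is 1.96 × √(0.18 × 0.82/1000) = 2.38 points, and 2.00/2.38 = 0.84. Over the grid the half-width runs from 1.68 (w = 8%) to 2.43 points (w = 19%). The gap is below one half-width in 7 of 12 cells.

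**Some replacements counted (q = 2%).**

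- The gap runs from 0.05 × (0.10 − 0.02) = 0.4 points to 0.20 × (0.20 − 0.02) = 3.6 points.
- The share of counted events that are not first implants is qp/[r(1 − p) + qp]. It runs from 0.001/0.191 = 0.52% (p = 5%, r = 20%) to 0.004/0.084 = 4.76% (p = 20%, r = 10%).
- The reported rate stays below the at-risk rate as long as q is below r.

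**Precision of the at-risk rate.** With n = 1000(1 − p), 1.96 × √[r(1 − r)/n] runs from 1.91 points (r = 10%, n = 950) to 2.77 points (r = 20%, n = 800). A reader who divides the whole-set interval by (1 − p) gets 1.91 to 2.84 points. Direct estimation therefore loses nothing against rescaling.

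**The case against.** The safety-set rate is a legitimate quantity. The study sets out to document outcomes in routine practice, Protocol 2.7.4 prescribes this population, and the SAP complies. The rate is unbiased for what it estimates and is low only as an estimate of something else. With no comparator or performance goal for this endpoint, its dependence on case mix matters mainly for comparisons outside the study. All of this stands, and it is why the safety-set rate should be kept.

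The missing event code is weak evidence on its own. A pacemaker implant is an intervention, and SAP 3.7.3.4 likewise identifies valve-related repeat procedures without a committee code. The unseen form may separate first implants from replacements. That is possible, but a rule that decides which events are counted belongs in the SAP.

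Part of the problem may be recoverable, because SAP 3.2 states: "Baseline demographic and clinical variables will be summarized for the attempted implant analysis set (safety set) as defined in section 3.4". If prior pacemaker appears there, a reader can approximate the at-risk rate. Neither document names it as a recorded item, however, and the approximation holds only if replacements are not counted.

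Finally, the size is assumed. The largest gap needs both extremes of the grid, and most cells fall below one half-width. That limits the importance of the point but does not alter the direction.

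**Conclusion.** The point holds, as a low-cost improvement to one descriptive secondary endpoint. The SAP fixes the denominator as everyone taken into the procedure room and leaves 'new' undefined. Followed exactly and with replacements not counted, it yields the at-risk rate diluted by the baseline pacemaker prevalence; the relative understatement equals that prevalence. In absolute terms the gap is 0.5 to 4.0 points over the assumed ranges, or 0.4 to 3.6 points if 2% of patients with a prior device have a replacement counted. Unlike sampling error, it does not shrink as the sample grows. These sizes are illustrations, because the documents supply neither prevalence nor event rate. The primary hypothesis, its test and the sample size are unaffected.

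**What to change.** - **SAP 3.7.4.3:** define 'new' as a first permanent pacemaker implanted during or after the procedure in a subject with none at baseline.
- **SAP 3.7.4.4:** keep the safety-set Kaplan-Meier rate. Add, as a supplementary estimate, the same SAP 3.5 analysis in safety-set subjects without a baseline pacemaker, and report both denominators. Both rates then use the same events and differ only in the denominator.
- **SAP 3.2:** add baseline pacemaker prevalence to the baseline summary.

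The cost is one definition, one subset analysis and one table line. Because the safety-set rate stays, the Protocol 2.7.4 population is not replaced and no deviation under Protocol 2.7 arises. The downside is a second, slightly higher rate with a somewhat wider interval.

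It must first be confirmed that prior pacemaker is recorded at baseline. The documents show only a general medical-history item and ECG data on rhythm and pacing indications. If it is not recorded, the at-risk rate cannot be produced and the report should state that as a limitation.

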3.8. Interim Analysis

No formal interim analysis is planned, and there are no plans for early termination of the study.

4. Revision Process

The study statistician will be responsible for execution of this statistical analysis plan, including any revisions and obtaining of appropriate approvals and distributions to the appropriate clinical staff.

5. Revision History

Version	Date	Author	Summary of Changes
1.0	08DEC2015	[name]	Initial Release
